5.5 Early Withdrawal of Subjects

5.5.1 *When and How to Withdraw Subjects*

- If at any time the patient develops unacceptable toxicity (e.g. a severe infusion reaction), as determined in consultation with the PI, he/she will be removed from the study treatment but should continue to be followed on the study for clinical outcomes including safety, intubation and mortality.
- If the patient withdraws consent for continued participation, he will be removed from study.

5.5.2 *Data Collection and Follow-up for Withdrawn Subjects*

If subjects withdraw prematurely from the study, follow-up will continue for all subjects. Subjects withdrawn because of unacceptable adverse events will be followed until resolution or stabilization of the adverse event. An attempt will be made to obtain survival information for all subjects for a period of at least 1 year following the time of registration or until death, whichever comes first. This will include attempts to contact subjects via telephone and by certified letter using information available to the investigators and the study team. When possible, at least two attempts will also be made to contact the subject's next of kin to obtain such information while observing relevant privacy laws, when applicable.

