7.6 Duration of Therapy

In the absence of treatment discontinuation due to adverse events, treatment may continue for up to 4 weeks or until one of the following criteria applies:

- Intercurrent illness that prevents further administration of treatment
- Unacceptable adverse events(s)
- Patient decides to withdraw from the study
- General or specific changes in the patient's condition render the patient unacceptable for further treatment in the judgment of the investigator
- Patient has been discharged from the hospital

At the end of the study period, Bristol-Myers Squibb Company will not continue to supply study drug to subjects/investigators unless the Sponsor-Investigator chooses to extend their study and such extension is approved by Bristol Myers Squibb Company. The investigator is responsible to ensure that the subject receives appropriate standard of care or other appropriate treatment in the independent medical judgement of the Investigator to treat the condition under study.

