7.8 Criteria for Removal from Study

Patients will be removed from study when any of the criteria listed in Section 8.6 applies. The reason for study removal and the date the patient was removed will be documented in the Case Report Form.

DOSING DELAYS/ DOSE MODIFICATIONS

7.9 **Criteria and Procedures for Dose Modifications and Interruptions**

Dose escalation/reduction is not permitted in this study in order to allow better evaluation of the safety and efficacy. However, if toxicities occur, subsequent doses of BMS-986253 should follow the below guidelines:

Toxicity	Grade	Hold Treatment (Y/N)	Timing of Treatment Restart	Dose Schedule for Treatment Restart	Discontinue Subject
	1, 2	No	N/A	N/A	N/A

Hematologic Toxicity	3, 4	Yes	Toxicity resolves to \leq Grade 1 or baseline	Restart at same dose. However, for all Grade 4 hematologic toxicities, treatment may not be restarted.	Toxicity does not resolve to \leq Grade 1 or baseline by the time of next treatment dose. Permanent discontinuation should be considered for any severe or life-threatening event.
Non-Hematologic Toxicity Note: Exception to be treated similar to Grade 1 toxicity: - Grade 2 fatigue - Grade 3 rash in patients who have not experienced a grade 3 drug-related skin AE	1	No	N/A	N/A	N/A
	2	Consider holding for persistent symptoms	Toxicity resolves to \leq Grade 1 or baseline	Restart at same dose	Toxicity does not resolve to \leq Grade 1 or baseline by the time of next treatment dose. Permanent discontinuation should be considered for any severe or life-threatening event
	3	Yes	Toxicity resolves to \leq Grade 1 or baseline	Restart at same dose	Toxicity does not resolve to \leq Grade 1 or baseline by the time of next treatment dose. Permanent discontinuation should be considered for any severe or life-threatening event
	4	Yes	Discontinue treatment	Treatment may not be restarted	Yes.

Criteria to resume treatment:

Subsequent dosing with study therapy may resume once AEs resolve to Grade 1 or baseline.

Participants experiencing AEs not meeting criteria for permanent discontinuation as outlined in **Section 5.5** may resume treatment with study medication under the following criteria:

- Participants may resume treatment with study treatment when the drug-related AE(s) resolve to Grade \leq 1 or baseline value, with the following exceptions:
 - Participants may resume treatment in the presence of Grade 2 fatigue.

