 - Participants who have not experienced a Grade 3 drug-related skin AE may resume treatment in the presence of Grade 2 skin toxicity.
 - Participants with Grade 2 uveitis, episcleritis, iritis, eye pain, or blurred vision (except for patients that do not respond to topical therapy and does not improve to Grade 1 severity within the re-treatment period OR requires systemic treatment).
- For participants with Grade 2 AST, ALT, or total bilirubin elevations, dosing may resume when laboratory values return to baseline and management with corticosteroids (if needed) is complete.
- Participants with combined Grade 2 AST/ALT and total bilirubin values with symptomatic liver inflammation (eg, right upper quadrant tenderness, jaundice) should have treatment permanently discontinued.

Exceptions to permanent discontinuation criteria:

The following exceptions to permanent discontinuation will apply:

- Grade 3 diarrhea, nausea, vomiting, or abdominal pain that returns to Grade 1 or baseline within 3 days with medical intervention.

- Grade 3 pruritus or rash that returns to Grade 1 or baseline within 7 days with medical intervention.
- Isolated Grade 3 or 4 electrolyte imbalances/abnormalities that are not associated with clinical sequelae and are corrected with supplementation/appropriate management within 3 days of their onset.
- Grade 4 neutropenia < 7 days in duration.
- Grade 4 lymphopenia or leukopenia.
- Grade 3 or 4 increase in amylase or lipase that is not associated with clinical or radiographic evidence of pancreatitis.
- Grade 3 infusion reactions that return to Grade 1 in < 6 hours.
- Grade 3 fever not associated with hemodynamic compromise (eg, hypotension, clinical, or laboratory evidence of impaired end-organ perfusion).
- Grade 3 tumor flare (defined as pain, irritation, or rash that localizes to sites of known or suspected tumor).
- Grade 3 fatigue.
- Grade 3 or 4 drug-related endocrinopathy AEs, such as adrenal insufficiency, adrenocorticotropic hormone, hyper- or hypothyroidism, or glucose intolerance, which resolve or adequately controlled with physiologic hormone replacement (corticosteroids, thyroid hormones) or glucose-controlling agents, respectively, may not require discontinuation after discussion with and approval from the Sponsor-Investigator.
- Any AE, laboratory abnormality, or concurrent illness, which, in the judgment of the investigator, presents a substantial clinical risk to the participant with continued study treatment dosing.

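### Section 7.9 fixes a permanent stop for symptomatic combined AST/ALT and bilirubin elevation at Grade 2 only; at Grade 3 the stop is conditional and discretionary

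*Combined protocol and SAP*

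**What the plan says.** Section 7.9 governs holding, restarting and stopping BMS-986253. It has three layers that bear on the liver.

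- **The dose-modification table.** A Grade 3 non-hematologic toxicity requires a hold. Treatment is discontinued if the toxicity has not resolved to "Grade 1 or baseline by the time of next treatment dose". If it has resolved, the entry is restart at the same dose. The discontinuation column adds: "Permanent discontinuation should be considered for any severe or life-threatening event". Grade 4 may not be restarted.
- **The criteria to resume treatment.** Two bullets concern the liver. One covers a single elevation: "For participants with Grade 2 AST, ALT, or total bilirubin elevations, dosing may resume when laboratory values return to baseline", with any corticosteroid management complete. The other covers the combined symptomatic picture: "Participants with combined Grade 2 AST/ALT and total bilirubin values with symptomatic liver inflammation" "should have treatment permanently discontinued". Both name Grade 2 only.
- **The closing paragraphs.** Any adverse event with clinical risk is assessed case by case between the investigator and the BMS Medical Monitor.

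For the permanent-discontinuation criteria themselves, Section 7.9 points elsewhere: "Participants experiencing AEs not meeting criteria for permanent discontinuation as outlined in" Section 5.5. The relevant text there reads: "If at any time the patient develops unacceptable toxicity (e.g. a severe infusion reaction), as determined in consultation with the PI". It contains no grade threshold and no liver criterion.

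**The concern.** A dosing rule should not become more permissive as the toxicity gets worse. The drafters judged that raised transaminases with raised bilirubin and symptoms of liver inflammation warrant ending treatment at Grade 2, with no condition about recovery. That reasoning applies at least as strongly at Grade 3, yet the written rule there depends on whether the values settle before the next dose and on someone's judgement.

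What is at stake is the individual patient's second or third dose. Under Section 7.1 the day-15 dose is given if the patient is still hospitalized, and the day-29 dose is optional for continued severe respiratory disease. A symptomatic combined Grade 3 event that settles before one of those days is the case the wording leaves open.

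**Working it through.** No arithmetic applies. The check sets the written rules side by side for one clinical picture: AST/ALT and total bilirubin raised together, with symptomatic liver inflammation.

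| Grade | Text that applies when read literally | Written consequence |
|---|---|---|
| Both values at Grade 2 | Combined symptomatic bullet, Section 7.9 | Permanent discontinuation, no condition attached |
| Either or both at Grade 3, neither at Grade 4 | Grade 3 non-hematologic row, Section 7.9 table | Hold; stop if unresolved by the next dose; otherwise restart at the same dose, with permanent discontinuation to be considered |
| Either at Grade 4 | Grade 4 non-hematologic row | Permanent discontinuation |

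The sequence is fixed stop, conditional restart, fixed stop.

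Next, is the Grade 3 cell filled by a fixed rule somewhere else?

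1. Section 5.5 is where Section 7.9 sends the reader. It turns on unacceptable toxicity as judged with the PI.
2. Section 7.6 ends treatment when changes in the patient's condition "render the patient unacceptable for further treatment in the judgment of the investigator". That is also judgement.
3. The last bullet of the list of exceptions to permanent discontinuation mentions substantial clinical risk in the investigator's judgement. It is discretionary, and it sits oddly in a list of reasons not to discontinue.
4. The case-by-case paragraph of Section 7.9 requires a review but does not fix its outcome.
5. The potential drug-induced liver injury definition in Section 8.2 and the 24-hour rule in Section 8.4.4 require reporting to BMS. Neither sets a dose.
6. The adverse events of special interest (Section 8.2), reporting to the DSMC (Section 8.4.3) and the continuous toxicity boundary (Section 11, Table 3) concern communication or the trial as a whole, not one patient's next infusion.

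None supplies a fixed individual stop for the Grade 3 picture.

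Finally, could Grade 2 simply be shorthand for Grade 2 and above? The protocol writes ranges where it wants them: the special-interest events in Section 8.2 start at Grade 3 and run upward, and the amylase and lipase exception in Section 7.9 names Grades 3 and 4. More important, the Grade 3 row is not silent. It gives an instruction of its own that differs from the bullet.

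**The case against.** Five points can be made on the other side.

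- **The Grade 2 bullet may catch the event as it resolves.** Values falling from Grade 3 to Grade 1 would normally pass through Grade 2, and Section 10.2 has bilirubin, ALT and AST measured daily in hospital. If both values are at Grade 2 while symptoms persist, the bullet applies on its own words; nothing limits it to the peak grade. Neighbouring bullets on fatigue and skin toxicity also concern the grade still present when re-dosing is decided. This stands, and it makes the gap narrow. It does not close it: symptoms may clear first, or the two values may not be at Grade 2 together.
- **Grade 3 does carry a stop.** A reader might infer that the plan has none. The documents do not support that: the hold is mandatory, and discontinuation follows if the event is unresolved by the next dose. Appendix A labels Grade 3 as severe, so the prompt to consider permanent discontinuation arises for every Grade 3 event. The Grade 2 bullet is itself worded as a recommendation. The difference between the grades is the condition attached, not the presence or absence of a rule.
- **The exceptions list implies a default.** Excusing certain Grade 3 events from permanent discontinuation suggests that others, including hepatic ones, would be discontinued. That may be the intent, but no such default is written, and it would contradict the table's restart entry. That supports clarifying the text.
- **Review is likely.** A reader might infer that patients would be re-dosed unreviewed. The case-by-case paragraph makes that unlikely. What remains is that a stop prescribed at Grade 2 is left to discretion at Grade 3.
- **The single-elevation bullet.** A reader might infer a second inversion: an isolated Grade 2 elevation must return to baseline, while Grade 3 may restart at Grade 1. That depends on whether the specific bullet or the general resume sentence governs. Under the general sentence the thresholds are equal, so this is not established and no change is asked for.

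**Conclusion.** The point holds as a wording gap in a dosing-safety rule. For combined symptomatic liver elevation, Grade 2 has a fixed permanent stop, while Grade 3 has a hold, a stop conditional on non-resolution, and otherwise a discretionary decision. It rests on a literal reading of the bullet; if site staff already read it as Grade 2 or higher, practice would not change.

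The effect is small and cannot be quantified. The documents give no liver-event rate in COVID-19 patients and no rate of hospitalization at day 15. Only the anti-IL-8 arm is exposed, with at most two re-dosing decisions per patient. A reader might look for consequences for the trial's conclusions; there are none, since the primary test, its alpha and the sample size do not depend on this rule. It is a cheap improvement for patient safety.

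**What to change.** In the criteria to resume treatment in Section 7.9, change the combined symptomatic bullet from 'combined Grade 2' to 'combined Grade 2 or higher'. Add one sentence saying that this bullet overrides the table's Grade 3 restart entry. Leave the single-elevation bullet, the Grade 3 hold and the Grade 4 stop as they are.

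The cost is an IRB-approved wording amendment. No tests are added, because the liver panel is already drawn daily in hospital. The downside is possibly a few missed day-15 or day-29 doses among patients whose Grade 3 event has resolved.

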
Even if the criteria to resume treatment are met, the consideration to re-initiate study therapy under the following exception will be made on a case by case basis after considering the overall benefit/risk profile, and in consultation between the investigator and the Sponsor. Any AE with clinical risk will be assessed on a case by case basis with the investigator and the BMS Medical Monitor, to determine the risks and benefits of continuing on therapy following resolution versus discontinuing therapy permanently.

All participants who discontinue IP should comply with protocol specified follow-up procedures as outlined in **Section 5.5**. The only exception to this requirement is when a participant withdraws consent for all study procedures including post treatment study follow-up or loses the ability to consent freely (e.g., imprisonment, involuntarily incarceration for the treatment of either a psychiatric or physical illness). If study treatment is discontinued prior to the participant's completion of the study, the reason for the discontinuation must be documented in the participant's medical records and entered on the appropriate case report form (CRF) page.

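### Section 7.9 lists events that the investigator judges a substantial risk under continued dosing as an exception to permanent discontinuation, against Sections 5.5.1 and 7.6 and the section's own toxicity table

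*Combined protocol and SAP*

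**What the plan says.** Section 7.9 (dose modifications and interruptions) contains a toxicity table, criteria for resuming treatment, and a list of exceptions introduced by "The following exceptions to permanent discontinuation will apply". The list has twelve bullets. A typical one is "Grade 3 infusion reactions that return to Grade 1 in < 6 hours". The twelfth is any adverse event, abnormal laboratory result or concurrent illness that the investigator judges "presents a substantial clinical risk to the participant with continued study treatment dosing".

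The paragraph after the list makes re-initiation a case-by-case decision and adds: "Any AE with clinical risk will be assessed on a case by case basis with the investigator and the BMS Medical Monitor". The stated aim of that assessment is to weigh continuing after resolution against stopping permanently.

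Three other places deal with the same kind of event:

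- **Section 5.5.1:** for a patient with unacceptable toxicity, "he/she will be removed from the study treatment but should continue to be followed" for outcomes.
- **Section 7.6:** treatment ends for unacceptable adverse events, or when changes in condition "render the patient unacceptable for further treatment in the judgment of the investigator".
- **Section 7.9, toxicity table:** "Permanent discontinuation should be considered for any severe or life-threatening event".

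**The concern.** The list exists to name events after which a patient need not come off treatment for good. An event that the investigator considers dangerous under continued dosing does not fit that purpose. Its presence there reverses the sense of the bullet relative to the heading above it.

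This is an operative safety rule, not background. The protocol's section on continuous toxicity monitoring describes the trial as the first test of an anti-IL-8 agent in severe COVID-19. The later doses go to patients who are still in hospital. Section 12.4 also requires the compliance coordinator to verify conduct against the written protocol, and for these events the written text does not give one consistent standard.

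**Working it through.** No figure in the plan bears on this point, so there is nothing to recompute. The check is a comparison of texts.

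**1. The bullet against its neighbours.** The other eleven bullets are named, specific events. Most carry a limiting condition: recovery within a stated number of hours or days, no clinical sequelae, or adequate control with treatment. A few, such as Grade 3 fatigue and Grade 4 lymphopenia or leukopenia, carry none but are still specific. The twelfth names no event and is defined only by judged risk from further dosing.

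**2. The bullet against the other provisions.**

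| Place | What judged risk or severe toxicity leads to |
|---|---|
| Section 7.9, last bullet under the exceptions heading | Exemption from permanent discontinuation |
| Section 5.5.1 | Removal from study treatment for unacceptable toxicity |
| Section 7.6 | End of treatment for unacceptable adverse events, or on the investigator's judgement |
| Section 7.9, toxicity table | Permanent discontinuation to be considered for severe or life-threatening events; no restart after Grade 4 non-hematologic toxicity |
| Section 7.9, paragraph after the list | Case-by-case assessment |

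The first row points the opposite way from the next three. Section 7.6 and the bullet even name the same decision-maker, the investigator, with opposite results.

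**3. Whether the paragraph after the list settles it.** It refers to re-initiation under an exception said to follow, but no exception follows. It could mean the bullet just above or the next sentence. One sentence names the sponsor as the party consulted and the next names the manufacturer's medical monitor. The assessment concerns continuing after resolution and does not say what applies before then. The bullet stays in the list.

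**4. Whether another list governs.** Section 7.9 refers to Section 5.5 for the criteria for permanent discontinuation, but Section 5.5.1 gives only unacceptable toxicity and withdrawal of consent. Section 7.8 refers to a Section 8.6, and Section 8 ends at 8.5. Neither reference supplies a rule that decides the matter.

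**5. Reach.** Section 7.1 schedules doses on Days 1, 15 and 29, so at most 3 − 1 = 2 later doses are open to a decision on discontinuation. Day 15 is given only to patients still hospitalized. Day 29 is optional and requires continued hospitalization with severe respiratory symptoms. Section 4.1 gives no further dose to patients discharged within two weeks of the first.

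**The case against.** A reader might infer that the protocol tells sites to keep dosing patients they believe to be in danger, or that it removes the safeguard for the highest-risk events. The documents do not support that. An exception to permanent discontinuation is not an instruction to dose. Sections 5.5.1 and 7.6 still provide for stopping, and the table holds treatment for most Grade 3 toxicity and for Grade 4. The paragraph after the list makes re-initiation a matter of overall benefit and risk even when the criteria for resuming are met. An investigator who judges the risk substantial has explicit authority to stop.

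A second argument is that the case-by-case paragraph is simply the procedure for this bullet: such events are neither automatically stopped nor automatically continued. The bullet just before it, on endocrine events, is also conditional on discussion and approval, so the list already holds one item that depends on consultation. This reading is plausible, and it makes it too strong to say that sites have no guidance. It is not certain, because the paragraph does not identify the exception it means and the heading still says the opposite.

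A third argument is that most clinicians would see the intent and stop treatment. Many probably would, but the rule then works only if its heading is ignored.

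What stands is that the consequence is limited. The contradiction in the text remains.

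**Conclusion.** Wrong as written: an internal contradiction in a safety rule. The last bullet under the exceptions heading conflicts with Sections 5.5.1 and 7.6 and with the toxicity table, and the paragraph that follows softens the conflict without resolving it.

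The practical reach is confined to the Day 15 and optional Day 29 doses in patients still hospitalized. Within that group the frequency cannot be derived from the documents. The point shows no effect on the primary endpoint, the error rates, the power or the analysis.

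The conclusion assumes that the printed layout is the intended one. That appears safe: the bullet is complete, sits at the same level as its neighbours, and has no intervening heading that would give it a different meaning.

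**What to change.** Reconcile the last bullet with its heading, with Sections 5.5.1 and 7.6, with the toxicity table and with the paragraph after the list. Moving or rewording the bullet is enough, so that events judged a substantial clinical risk carry one unambiguous instruction. Which instruction that is belongs to the clinical team. In the same edit, state which exception the following paragraph refers to and who is consulted, and correct the references to Sections 5.5 and 8.6.

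A separate conflict in the same list also needs reconciling. The list exempts Grade 4 neutropenia lasting under 7 days and Grade 4 lymphopenia or leukopenia, while the table bars restart after every Grade 4 hematologic toxicity.

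The cost is a short text amendment, with no change to sample size, data collection or analysis.
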